1 - **HUMAN SUBJECTS RESEARCH PROTOCOL**

2 **COVER PAGE**

3

4

5

6

7

8 **Official Study Title:** Enhancing Prolonged Exposure with Cannabidiol to

9 Treat PTSD

10

11 **NCT number:** NCT05132699

12

13 **IRB Approval Date:** 11-15-2022

14

15

16 **Unique Protocol ID:** HSC20210711H

17

18

19

20

21

22

23

24

25

26

27

28

29

30

31

32

33

34

35

36

37

38

39

40

41

42

43

44 **1. PROTOCOL TITLE:** Enhancing Prolonged Exposure with Cannabidiol to Treat PTSD45 **2. ABSTRACT**

46 Posttraumatic stress disorder (PTSD) is considered a signature psychiatric disorder among military populations. When left
47 untreated, the symptoms of PTSD can cause significant health and functional impairments. While established treatments
48 for PTSD exist, there remains room for improvement in outcomes since almost half of military patients fail to benefit from
49 treatment. Epidiolex (Cannabidiol [CBD]) is an FDA-approved, non-controlled prescription medication with promising
50 potential for the treatment of PTSD.^{1,2} To date, there are no published clinical trials investigating CBD in reducing PTSD,
51 and existing literature in humans with PTSD only includes healthy individuals or case study data. Greater research is
52 needed to fully understand the benefits of CBD for PTSD and to better understand biological mechanisms for its effect.
53 The primary goal of this pilot project is to demonstrate the safety and feasibility of using CBD in combination with standard
54 of care prolonged exposure (PE) psychotherapy to reduce PTSD symptoms (Aim 1). We will also assess possible
55 biochemical and physiological outcomes associated with treatment (Aim 2) and evaluate the relationship between
56 changes in biochemical/physiological measures with PTSD symptom reductions (Aim 3). To address study aims, we will
57 enroll 24 individuals with PTSD to be randomized to CBD (n=12) or placebo (n=12) and all participants will receive 10
58 daily sessions of PE.

60 **3. OBJECTIVES/SPECIFIC AIMS/RESEARCH QUESTIONS**

61 This project will be a pilot, double-blind randomized controlled trial of CBD effects to pursue three goals: (1) to
62 demonstrate the safety and feasibility of using CBD to reduce PTSD symptoms in conjunction with massed PE (mPE); (2)
63 to assess biochemical and physiological outcomes associated with PTSD treatment; and (3) to evaluate the possible
64 relationship between changes in biochemical/physiological measures with PTSD symptom reductions.

65 **Aim 1:** To examine the safety, feasibility, and PTSD symptom reductions associated with CBD (n=12) vs. placebo (n=12)
66 in 24 individuals receiving 10 daily sessions of mPE as a standard of care for PTSD.

67 Hypothesis 1: Combining CBD with mPE will be safe based on minimal (< 5%) adverse events and no serious adverse
68 events related to treatment in the study.

69 Hypothesis 2: A CBD vs. placebo trial design will be feasible defined as 75% or more of assessed individuals meeting
70 all eligibility criteria and 80% or more of CBD participants completing all 10 mPE sessions.

71 Hypothesis 3: Participants in the CBD condition will have greater treatment-related PTSD reductions than placebo as
72 measured by the Clinician Administered PTSD Scale (CAPS-5)³ and PTSD Checklist (PCL-5).⁴

73 **Aim 2:** To evaluate biochemical and physiological levels associated with the eCB system and stress response in CBD vs.
74 placebo.

75 Hypothesis 4: Participants in the CBD condition will have higher levels of AEA and 2-AG, and lower levels of cortisol
76 than placebo following treatment.

77 Hypothesis 5: Participants in the CBD condition will have lower average heart rate during exposure therapy sessions
78 than placebo.

79 **Aim 3:** To determine the association between changes in biomarker levels (cortisol, AEA, 2-AG), physiology (heart rate),
80 and PTSD symptom reduction following treatment.

81 Hypothesis 6: Reductions in cortisol and increases in AEA and 2-AG will be associated with PTSD symptom reductions
82 following treatment.

83 Hypothesis 7: Lower average heart rate observed during exposure therapy sessions will be associated with PTSD
84 symptom reductions following treatment.

85 **4. MILITARY RELEVANCE**

86 As compared to civilians, the rate of PTSD is particularly elevated among military populations, with approximately 23% of
87 military vs. 6-8% of civilians meeting criteria for PTSD.⁵ PTSD has been identified as the signature deployment-related
88 psychiatric condition among service members. The functional impact of PTSD can cost service members their military
89 careers and veterans with PTSD are at increased risk of unemployment and homelessness following military separation.⁶
90 Notwithstanding evidence that PE is an effective treatment for PTSD, there remains room for improvement in outcomes
91 given that a large proportion of patients (~50%) fail to significantly benefit from treatment.⁷ This issue is especially
92 problematic among military populations who generally demonstrate poorer treatment gains from first-line psychotherapies
93 for PTSD including PE.^{8,9} Given that almost three million U.S. military service members have deployed to Afghanistan,
94 Iraq, and surrounding locations in support of military combat operations since September 11, 2001, the need for effective
95 treatment for PTSD is critical. Research dedicated to target mechanisms associated with PTSD symptomatology has the
96

97 potential to promote greater PTSD treatment efficacy that will lead to greater symptom reductions, positive well-being, and
98 improved functioning in civilians and military veterans.

99 **5. BACKGROUND AND SIGNIFICANCE**

100 **PTSD Prevalence and Impact.** PTSD is a chronic and debilitating condition triggered by exposure to a traumatic event.
101 Symptoms of PTSD can include anxiety, negative mood, sleep disruption, nightmares, and negative, uncontrollable
102 thoughts about the event. When left untreated, it can lead to detriments in mental health and psychosocial functioning.^{10,11}
103 The overall impact of PTSD is substantial and often leads to significant burdens on the individual, their family, and the
104 community.¹² The sequelae of PTSD not only impacts an individual's immediate environment but also places significant
105 burden on society due to increased work sick days and greater healthcare utilization.^{6,11} The rate of PTSD is particularly
106 elevated among military populations, with approximately 23% of military meeting criteria for PTSD annually.⁵ PTSD has
107 been identified as the signature deployment-related psychiatric condition among service members. The functional impact
108 of PTSD can cost service members their military careers and veterans with PTSD are at increased risk of unemployment
109 and homelessness following military separation. Given that almost three million U.S. military service members have
110 deployed to Afghanistan, Iraq, and surrounding locations in support of military combat operations since September 11,
111 2001, the need for effective treatment for PTSD is critical.

112 **Behavioral Therapy Approaches to PTSD Treatment.** Evidence-based treatments for PTSD exist and are well-
113 established.¹³ PE is a type of Cognitive Behavioral Therapy (CBT) and one of the most widely used first-line interventions
114 for PTSD. PE has been validated across various populations and trauma types, e.g.,¹⁴⁻¹⁶ Preliminary evidence suggests that
115 PE can even be effectively delivered in deployed settings, potentially helping service members return to duty without
116 being aeromedically evacuated out of theater.¹⁷ PE aims to reduce trauma-related distress and PTSD symptomatology
117 through extinction learning interventions (i.e., repeated exposure) to internal (e.g., trauma memory) and external (e.g.,
118 environmental stimuli) trauma cues under objectively safe conditions. Notwithstanding evidence that PE is an effective
119 treatment for PTSD, there remains room for improvement in outcomes given that a large proportion of patients (~50%) fail
120 to significantly benefit from treatment.⁷ This issue is especially problematic among military populations who generally
121 demonstrate poorer treatment gains from first-line psychotherapies for PTSD including PE.⁹ Based on the rising number of
122 service members returning from combat deployments to Afghanistan, Iraq, and surrounding areas, there is a high priority
123 need for the most effective treatments for PTSD. Research dedicated to target mechanisms associated with PTSD
124 symptomatology has the potential to promote greater PTSD treatment efficacy that will lead to greater symptom
125 reductions, positive well-being, and improved functioning in civilians and military veterans.

126 **Medication Approaches to PTSD Treatment.** Despite the benefits of first-line CBT interventions for PTSD treatment,
127 pharmacotherapy remains the most commonly used approach to treat PTSD in civilians and military veterans.¹⁸ The only
128 pharmacological interventions for PTSD approved by the Food and Drug Administration (FDA) are the selective serotonin
129 reuptake inhibitors (SSRIs) fluoxetine and sertraline. Although approved by the FDA for PTSD treatment, these drugs
130 have relatively modest benefits to reduce PTSD and often fail to help patients reach PTSD remission.^{19,20} Based upon
131 expert panel psychological trauma recommendation guidelines²¹, no medication treatments have been determined to be a
132 first-line option for treatment of PTSD. Unfortunately, this state of pharmacotherapy for PTSD has prompted many
133 providers to use polypharmacy in which patients are prescribed a combination of medications with little to no empirical
134 guidance on either the benefits or adverse reactions.²²

135 **Endocannabinoid System and PTSD.** One potential reason for the low efficacy of SSRIs and the use of
136 polypharmacotherapy is that these medications do not directly target PTSD symptomatology. A rapidly growing body of
137 evidence has highlighted the endocannabinoid (eCB) system as a critical regulator of the stress response.²³ Further, it has
138 been suggested that psychological trauma can lead to long-term alterations in the eCB system.²⁴ The eCB system is a
139 neuromodulatory system comprised of two primary receptors (CB1 and CB2), two main neurotransmitters (anandamide
140 [AEA] and 2-arachidonylglycerol [2-AG]), and several enzymes that synthesize and degrade these neurotransmitters.²⁵
141 Most research has focused on CB1 receptors, which are primarily located in the central nervous system and have the
142 highest densities in brain regions associated with anxiety and fear learning (e.g., cortex, amygdala, and hippocampus).
143 Preclinical animal models have shown that CB1 antagonists increase anxiety, while agonists produce anxiolytic effects.²⁶
144 AEA and 2-AG are the two primary endogenous eCBs that act as agonists at CB1 receptors.^{27,28} These eCBs are critical
145 nerve signaling chemicals shown to regulate mood, memory, perception, and sleep.²⁹ Overall, novel pharmacological
146 approaches targeting the eCB system have promising potential to improve anxiety, mood, and sleep problems, while
147 facilitating extinction learning, all of which characterize PTSD symptoms and seem particularly important to compliment
148 first-line psychotherapy interventions.

149 **Cannabidiol for Augmentation of PE Treatment for PTSD.** Based on growing evidence on the synergistic relationship
150 between the eCB system and PTSD, increasing efforts have been devoted to pharmacotherapy options. The recently
151 FDA-approved prescription medication, Epidiolex (Cannabidiol [CBD]) is a cannabis-derived, non-controlled drug that may

152 be beneficial for PTSD. Existing research has shown that CBD may facilitate extinction learning, decrease anxiety, and
153 improve mood and sleep, all of which might enhance the effectiveness of mPE for PTSD.^{30,31} Furthermore, CBD is well
154 tolerated, even in large doses, and has not been shown to produce adverse side effects associated with other cannabis-
155 derived medications (e.g., dependence, withdrawal, psychoactive effects, increased anxiety, memory and concentration
156 difficulties, slowed reaction time, coordination problems, and elevated heart rate). Thus, CBD may be able to maximize
157 the positive benefits associated with the eCB system, while mitigating adverse events that occur with other cannabis-
158 derived drugs.

159 Most of the existing literature indicating the benefits of CBD for PTSD treatment has involved preclinical animal studies,
160 case studies, and a few proof-of-concept trials with healthy humans. Preclinical animal models have used a fear-based
161 conditioning paradigm^{e.g.,32} designed to parallel the impact of trauma in humans with PTSD to investigate the effects of
162 CBD. Animal models have shown that CBD can reduce cardiovascular and anxiogenic effects of stress.^{30,31} CBD has
163 been found to decrease retrieval and acquisition of fear memories^{33,34} and even block reconsolidation of the trauma
164 memory in animal models.³⁰ The most promising outcome of preclinical PTSD research is evidence that CBD can facilitate
165 and enhance the extinction learning process, a key component of exposure-based psychotherapies for PTSD.^{35,36}
166 Consistent with preclinical animal research, Das et al.³⁷ found that CBD facilitated extinction learning and decreased cue-
167 based fear response in a sample of healthy humans.

168 Only a few studies have been completed in humans. A case report found that daily use of CBD was associated with
169 reduced anxiety and improved sleep in a child with treatment resistant PTSD despite the fact that standard
170 pharmacotherapy for PTSD had produced only limited and acute symptom relief.³⁸ In a retrospective case series analysis
171 of adults (N=11) with PTSD, participants received oral CBD in combination with routine psychiatric and psychotherapy
172 care over 8 weeks.² Results suggested that CBD was associated with a 28% decrease in PTSD symptom and was well
173 tolerated (with no discontinuation due to side effects) among participants. Though these findings suggest that CBD may
174 be used for the treatment of PTSD, there is a paucity of research on the safety, feasibility, and efficacy of CBD as a
175 treatment for PTSD in human trials.

176 Furthermore, although preliminary evidence suggests CBD may benefit PTSD symptom reduction, the specific
177 mechanisms of action of CBD on the eCB remains unclear. One possible mechanism may include modulation of the eCB
178 system since research has shown that CBD may have low affinity for CB receptors, but nonetheless is able to bind to
179 CB1.³⁹ CBD may also act as an antagonist to other agonists due to effects at different prejunctional sites and indirect
180 interactions with non-cannabinoid receptors.⁴⁰ In turn, this may explain possible effects on eCB metabolism including
181 inhibition of the uptake and degradation of critical eCBs associated with stress response including AEA and 2-AG.

[figure not shown]
182 **Innovation.** Additional research is warranted to fully understand the benefits of CBD for PTSD. Currently, there are no
183 published clinical trials investigating the efficacy of CBD in reducing PTSD and existing PTSD literature in humans only
184 includes healthy individuals or case study data. Research on cannabinoids and PTSD remains in the early stages of
185 development and more research is needed to understand how CBD modulates the eCB system. Based on existing
186 research, the next logical step is to investigate CBD as an augmentation treatment for an established psychotherapy that
187 targets extinction learning mechanisms for PTSD symptom reduction. This proposal will examine CBD as an adjunct for
188 mPE and explore potential biological mechanisms for its effect, making it the first study of its kind. Findings from this study
189 have the potential to improve outcomes among military and civilians with PTSD and mitigate the personal, social, and
190 economic costs of this debilitating, chronic condition. This study will also expand understanding of the relationship
191 between PTSD, CBD, and the eCB system.

192 6. RESEARCH DESIGN

193 This study is an early Phase II double-blind, pilot randomized controlled clinical trial. We will use a permuted block
194 randomization design stratified by PTSD severity median score of 51 on the PCL-5 and population type (military or
195 civilian). The median score stratification was derived from a recently completed STRONG STAR randomized clinical trial
196 of military veterans seeking treatment for PTSD (manuscript in press). The decision to stratify by population was based on
197 existing literature that has found differences in treatment response between military and civilian samples (e.g., Steenkamp
198 et al., 2015; [name] et al., 2019). Participants will be 24 individuals with PTSD to investigate the safety, feasibility, and
199 PTSD symptom change associated with CBD 250mg taken twice a day for 18days (n=12) vs. placebo (n=12) in
200 combination with a standard of care, 10-sessions mPE psychotherapy administered over 2 weeks. Aims 2 and 3 will
201 evaluate biochemical and physiological outcomes associated with eCB and PTSD that may be affected by CBD.
202 Permuted block randomization is advantageous in small clinical trials to ensure equal allocation of participants in each
203 condition. Participant randomization will be subdivided into randomized blocks of four, two patients in each block will be
204 assigned to CBD and two will be assigned to placebo. Randomization will occur after the participant consents to the study
205 and eligibility is determined. [name] (Co-Mentor on this KL2) will determine randomization codes and
206 coordinate with the compounding pharmacy (Oakdell Pharmacy) providing the medication and placebo for this trial to
21-711H, [name], Form BB, 11-15-22, AMD.docx

207 ensure blocking procedures are appropriately carried out. All other study team members will be blinded to randomization.
 208 The study assessments and the timing for repeated assessments conducted are described in detail in section 7.3.

Figure 1. General Study Design Overview

Notes. See Section 7.3 for detailed study procedures.

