7. RESEARCH PLAN

7.1 Selection of Subjects

Number of subjects to be screened for eligibility: 40

Target number randomized: 28

Target enrollment number for completers: 24

7.1.1. Subject Population.

Individuals between 18-65 years old recruited from the San Antonio community will be invited to participate in this research.

Efforts will be tailored to equally recruit diverse individuals across sex, gender/sexual orientation, race, age, disability, socioeconomic status, national origin, and branch of military service.

7.1.2. Inclusion and Exclusion Criteria.

Inclusion Criteria

1. Individuals between the age of 18 to 65 years old at time of screening.
2. Able to write, read, and speak English
3. PTSD diagnosis as assessed by Clinician-Administered Posttraumatic Stress Scale (CAPS-5)
4. Stable medication regimen for at least four weeks prior to the onset of study participation.

Exclusion Criteria

1. History of opiate, cocaine, methamphetamine, benzodiazepine, or cannabis abuse as determined by the National Institute of Drug Abuse Quick Screen (NIDA-Q).
2. Currently using opiates, cocaine, methamphetamines, benzodiazepines, or cannabis as evidenced by a positive urine drug screen prior to enrollment.
3. Currently pregnant as determined by a positive urine pregnancy test prior to enrollment.
4. Current clinically significant alcohol abuse in the past two weeks on the Quick Drinking Screen (QDS).
5. Currently breastfeeding.

238 6. Ongoing illness or physical health problem(s) that may be exacerbated by CBD (e.g., history of liver problems)
239 7. History of significant allergic condition, significant drug-related hypersensitivity, or allergic reaction to
240 cannabinoids.
241 8. Regular use of the following concomitant medications because of the possible interaction with CBD
242 • The anti-convulsant/anti-epileptics Carbamazepine and Phenytoin
243 • The atypical antipsychotics Olanzapine, Quetiapine, and Risperidone
244 • The entire class of barbiturates (Sedative-Hypnotics)
245 • Chronic, daily use of any class of benzodiazepines. Intermittent or as needed dose of a benzodiazepine will
246 be allowed.
247 • The miscellaneous hypnotics Zaleplon, Zolpidem, Eszopiclone, Ramelteon, and Suvorexant
248 • The herbal supplement St. John's Wort.
249 • The entire class of glucocorticoids
250 • Use of platelet inhibitors Clopidogrel and Warfarin unless the participant is on a stable dose.
251 • The antiretrovirals Ritonavir and Indinavir

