450 devices are monitored by state-of-the-art monitoring applications that include configuration audit, management, and
451 availability 24x7.

458 The UTHSA STRONG STAR data server is currently a VMware Instance running Windows Server 2016 Enterprise
 459 Standard with daily backup services and vSphere Business Continuity Advanced Failover.

460
 461 Only select STRONG STAR Data and Statistics Services personnel have direct access to the data on a "need to access
 462 basis"; for example (but not limited to) detecting and repairing data corruption and producing reports not currently within
 463 the STRONG STAR system. STRONG STAR Data and Statistics Services also follows the Principles Of Least Privilege
 464 (POLP). All user activity is tracked and recorded within the system so if any records are added, altered, or viewed the
 465 action is recorded and can be recalled for auditing purposes. Access to this information will require a password-protected
 466 login available only to authorized STRONG STAR Data and Statistics Services staff.

467
 468 Every member of the Research Team will be trained and monitored about how to handle and protect both medical and
 469 research records. Furthermore, the Research Team strictly controls access to study data.

470
 471 The STRONG STAR Data Safety and Monitoring Plan (DSMP) that has been developed in accordance with the National
 472 Institutes of Health Office of Human Research Protection to assure the appropriate clinical safety monitoring of study
 473 subjects participating in research will be used to monitor this study.

474 475 7.4. Statistical Consideration

476 477 7.4.1. Sample Size Estimation.

Estimate Required Sample Size (Completed / Evaluable)	24
Estimate Participant Drop Out / Withdrawal after Randomization/Inclusion	4 (17%)
Total Required to Randomize / Include	28
Estimate Participant Screen Fail / Exclusion	12 (30%)
Total Required to Consent	40

478
 479 7.4.2. Primary (i.e., primary outcome variables) and secondary endpoints
 480 **Health Questionnaire and Self-Report Measures:** The primary aim of this pilot is to explore the potential feasibility,
 481 safety, and effect of CBD in reducing PTSD symptoms compared to placebo in retired service members receiving mPE.
 482 Therefore, the primary outcome variables will be the CAPS-5 total score, the PCL-5 total score, and adverse event

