 483 monitoring. Secondary endpoints are listed in the table in Section 7.3 and include associated psychopathology, such as
 484 severity scores on measures of depression, general anxiety, disability, and PTSD-related cognitions.

485 **Biospecimens & Heart Rate Monitoring Measures:** We will also assess possible biochemical and physiological
 486 outcomes associated with treatment (Aim 2) and evaluate the relationship between changes in biochemical/physiological
 487 measures with PTSD symptom reductions (Aim 3). To address these aims we will collect blood and saliva samples and
 488 heart monitoring data via a wearable device as described in 7.3.1

489 7.4.3. Data analysis.

490 This pilot study was not powered for formal efficacy or mechanistic hypotheses testing.⁴² Our primary interests are to evaluate
 491 the safety and feasibility of the proposed recruitment, assessment, and treatment protocols; and to detect a signal of possible
 492 PTSD symptom reductions associated with CBD in preparation for a larger trial. To inform future studies, we will calculate
 493 conventional effect sizes with 95% confidence interval limits. Hedges' g will be used to calculate continuous outcome effect
 494 sizes (e.g., CAPS-5, PCL-5). Hedges' g has been recommended over Cohen's d for small samples based on sample size
 495 adjustments yet can be interpreted using the same conventional recommendations as Cohen's d.⁴³

496 Although the statistical power of this study is limited, we will perform statistical analyses appropriate for an adequately
 497 powered study to identify data analysis issues germane to future planning (e.g., data management and scoring, missing
 498 data, data distributions, outliers, trends over time, covariance structures). Statistical analyses will be intent to treat. We will
 499 complete descriptive statistics to describe the study sample and address the feasibility and safety hypotheses. Continuous
 500 outcome measures related to symptom changes and comparison of baseline and posttreatment means will be done with
 501 general or generalized linear mixed effects regression models with repeated measures, with fixed effects of time, group,
 502 and the group by time interaction. Measures with data collected during treatment will also be included in models. Little's⁴⁴
 503 missing completely at random analysis will be completed to confirm likelihood-based model assumptions. Pearson

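### Hypothesis 1 declares CBD plus mPE safe below 5% adverse events without defining what is counted, in whom, or out of what; on either participant-level reading the cutoff cannot support a demonstration of safety

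*Combined protocol and SAP*

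**What the plan says.** Section 3, Aim 1, Hypothesis 1 states: "Combining CBD with mPE will be safe based on minimal (< 5%) adverse events and no serious adverse", and on the next line "events related to treatment in the study". Hypothesis 2, directly below, names its unit and arm (CBD participants) for session completion. Hypothesis 1 does neither for the 5%.

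The stated ambition varies by section:

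- **Abstract:** "The primary goal of this pilot project is to demonstrate the safety and feasibility of using CBD in combination with standard". The opening of section 3 repeats the verb *demonstrate*.
- **Aim 1:** the verb is *examine*.
- **Section 7.4.2:** the primary aim is to *explore* feasibility, safety and effect. The same paragraph makes adverse events a primary outcome: "the primary outcome variables will be the CAPS-5 total score, the PCL-5 total score, and adverse event" monitoring.
- **Section 7.4.3:** the interest is to *evaluate* safety, and the team will "complete descriptive statistics to describe the study sample and address the feasibility and safety hypotheses".

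Section 7.4.3 also promises "conventional effect sizes with 95% confidence interval limits", but names a method (Hedges' g) only for continuous outcomes. Its disclaimer, "This pilot study was not powered for formal efficacy or mechanistic hypotheses testing", does not mention safety.

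Section 8.1 places common CBD effects such as fatigue, drowsiness and diarrhea under a heading for likely but non-serious risks. It also describes CBD adverse events as minimal and gives no overall rate. Section 9.1 refers adverse event assessment to a consortium SOP and IRB policy.

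**The concern.** A rule that attaches the word safe to a percentage needs a numerator, a denominator, an arm and a relatedness rule. Hypothesis 1 has none of these for its 5%. It is also unclear whether relatedness limits all adverse events or only the serious ones, and whether treatment means CBD, mPE or both. Those choices could be made after the data are seen, and they can reverse the verdict.

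Even with the definitions fixed at participant level, an arm of 12 to 14 is too small for a 5% cutoff to separate acceptable from unacceptable rates. Adverse events are a primary outcome and the pilot is meant to prepare for a larger trial. An unsupported safe or not-safe label would therefore be carried forward.

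**Working it through.** **Inputs.** 12 per arm and 24 in total (Abstract; Aim 1). "Target number randomized: 28" (section 7.1). Four expected dropouts, given as 17% (section 7.4.1). Allocation 1:1 in blocks of four, within strata defined by two binary factors (section 6). Ten mPE sessions per participant. Four scheduled adverse event checks: PE sessions 1, 5 and 10, and the 1-month follow-up (section 8.1).

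**The plan's own figure.** 24 + 4 = 28, with 4/24 = 16.7%, shown as 17%. An equal split gives 28/2 = 14 per arm, which is my assumption. The documents give no calculation behind the 5%, so there is none to reproduce.

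**Reading A: CBD-arm participants with an adverse event.** 1/12 = 8.3% and 1/14 = 7.1%, so one affected participant fails and the rule allows zero. One participant falls below 5% only if 1/n < 0.05, that is n ≥ 21. Chance imbalance does not reach that. Four strata could each end on a half-filled block with two extra CBD assignments, giving at most 10 + 8 = 18 CBD participants of 28.

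Exact (Clopper–Pearson) limits. At zero events the two-sided 95% upper limit is 1 − 0.025^(1/n), and the one-sided limit is 1 − 0.05^(1/n).

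| Result | Verdict under the rule | Two-sided 95% CI | One-sided 95% upper limit |
|---|---|---|---|
| 0/12 | passes | 0–26.5% | 22.1% |
| 0/14 | passes | 0–23.2% | 19.3% |
| 1/12 | fails | 0.2–38.5% | – |
| 1/14 | fails | 0.2–33.9% | – |

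The probability of passing is (1 − p)^n. The documents give no overall rate, so p is assumed:

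| Assumed true rate p | n = 12 | n = 14 |
|---|---|---|
| 3% | 69% | 65% |
| 5% | 54% | 49% |
| 10% | 28% | 23% |
| 20% | 7% | 4% |

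At a true rate exactly on the limit, the verdict is close to a coin toss. At 3%, below the limit, it still fails 31% (35%) of the time.

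**Reading B: participants in both arms pooled.** 1/24 = 4.2% and 1/28 = 3.6% pass; 2/24 = 8.3% and 2/28 = 7.1% fail. At one event the two-sided upper limit is 21.1% (n = 24) or 18.3% (n = 28). At an assumed 10% in both arms, the rule passes 29% or 22% of the time. This reading also mixes in placebo participants.

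**Reading C: events per mPE session, CBD arm.** Denominator 12 × 10 = 120 or 14 × 10 = 140. 5/120 = 4.2% and 6/140 = 4.3% pass; 6/120 and 7/140 equal 5.0% and fail.

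**Reading D: events per scheduled check, CBD arm.** Denominator 12 × 4 = 48 or 14 × 4 = 56. 2/48 = 4.2% and 2/56 = 3.6% pass; 3/48 = 6.3% and 3/56 = 5.4% fail.

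**Side by side.** Suppose one CBD participant has one qualifying event and nothing else occurs. Reading A says not safe; B, C and D say the criterion is met.

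**The case against.** The strongest reply is that this is a pilot using a descriptive benchmark. Nothing in the protocol says that meeting the 5% excludes a true rate of 5%. Wide intervals are unavoidable at 12 per arm. Aim 1, section 7.4.2 and section 7.4.3 already speak of examining, exploring and evaluating, and the safety hypothesis is assigned to descriptive statistics. Participant protection does not run through Hypothesis 1: the protocol has a data safety monitoring plan, scheduled checks, weekly adverse event review and discontinuation criteria. The SOP, which is not available here, may define relatedness.

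Much of that stands, and it limits the weight of the point. It does not remove it. Hypothesis 1 still ties a numerical cutoff to the statement that the combination will be safe, and section 7.4.3 says the descriptive statistics will address that hypothesis. The Abstract and the opening of section 3 still promise a demonstration. An SOP could settle relatedness, but the arm and denominator behind the 5% belong with the hypothesis.

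A reader might infer three stronger things that the documents do not support:

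- **That the rule simply means zero adverse events.** This holds only on Reading A. The reference to combining CBD with mPE points to the CBD arm, but the text counts adverse events, not participants, and its closing words could cover the whole study.
- **That Hypothesis 1 is bound to fail because section 8.1 lists likely effects.** That section gives no overall rate and calls adverse events minimal. All that follows is that, on Reading A, one participant with one such qualifying event is enough to fail.
- **That oversight of participants is deficient.** No stopping or go/no-go rule uses the 5%.

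**Conclusion.** The point holds as an undefined safety criterion joined to a conclusion it cannot carry. Which verdict the rule gives depends on a unit, arm, denominator and relatedness rule that the protocol leaves open.

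On either participant-level reading, a pass does not demonstrate safety. It leaves adverse event rates up to 26.5% (23.2%) compatible with the data in the CBD arm, or up to 21.1% (18.3%) pooled at one event. For the CBD arm that is roughly five times the 5% limit two-sided, or about four times on the one-sided limits of 22.1% (19.3%). A CBD-arm failure at one participant does not show a rate above 5% either.

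The limits rest only on the stated sample sizes and an equal split of the 28. The pass probabilities rest on assumed rates. The consequence is confined to the safety conclusion reported and carried into the larger trial. The point should be fixed, but it does not threaten the conduct of the pilot.

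**What to change.** In Hypothesis 1 and section 7.4.3:

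1. Drop the below-5% declaration of safety. Alternatively, keep 5% only as a descriptive benchmark with unit, arm, denominator and relatedness rule defined, stating whether relatedness is to CBD, mPE or either, and citing the SOP if it supplies the definition.
2. Among randomized participants, report by arm the proportion with at least one adverse event of any cause and the proportion with any serious adverse event, each with an exact 95% CI. Add the CBD-minus-placebo difference with a small-sample 95% CI whose method is named in advance. Any-cause counts keep the main table free of attribution judgments; show related events and related serious events as a secondary breakdown.
3. State in advance that zero events in 12 (14) excludes only rates above about 26% (23%).
4. Align *demonstrate* in the Abstract and section 3, and the will-be-safe wording in Hypothesis 1, with the *examine* and *explore* language already used in Aim 1 and section 7.4.2.

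The cost is protocol wording and one small table, with no added participants, visits or data. The downside for the team is a less favourable safety claim.
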